### 6.3 Treatment Visits

Treatment visit schedules for data collection do not differ by group assignment. For the purpose of data collection and event ascertainment all participants will have post-randomization visits, at month 6 (+/- 30 days), and every 6 months (+/- 30 days) thereafter. During all treatment visits, blood pressures will be recorded in a sitting position. Patients will be asked for the occurrence of adverse events and (reasons) of admissions to hospitals and visits to outpatient clinics, quality of life (EQ-5D-5L), information regarding concomitant medication, and the cardiovascular outcome are retrieved. All subsequent CTAs/MRAs of the aneurysm which are made as part of standard care will be uploaded in a pseudonymised manner to a central server.

Patients of the intervention group will be asked to have the blood-pressure device with them, to permit a readout of the blood-pressure values to a tablet computer at the trial centre. In case patients did not yet transfer the blood pressure measurements to the central database using their own smartphone, the investigator can transmit available measurements in a pseudonymized fashion via a secure online connection to the central database at the sponsor's institution (University Medicine Mannheim). The investigator will see a displayed graph at the tablet computer and will categorize the findings into one of these three classifications:

- The blood pressure is satisfactory or lower,
- The blood pressure is higher than recommended,
- The blood pressure is not checked at least once a week

Based on the available blood pressure data, the investigator will decide whether or not the patient should see a GP for optimisation of blood pressure treatment. If the blood pressure is not checked at least once a week, patients are reinstructed how to use the device.

Blood pressure data obtained by the electronic device are not subject to clinical monitoring.

For the control group, a visit could be replaced by a telephone visit, if the previous visit was performed at the trial center.

In the event that the Covid-19 pandemia would cause circumstances in which the treatment visits need to be cancelled, the scheduled trial visit can be replaced by a telephone visit. The blood pressure readout of the devices of the intervention group would be skipped then until the next visit at the center.

CTAs/MRAs beyond this time point will also be uploaded to the central server. We will collect data on GFR and blood sodium in patients with pre-existing, compensated chronic renal failure (stage III: GFR <60 mL/min/1.73 m^2), who are monitored for these parameters by their treating physicians. During all trial visits the investigators will stress that smoking cessation is pivotal and inform patients who smoke about possible options for help in smoking cessation. The number of cigarettes per day and alcohol consumption per day will be recorded. The investigator will collect data on GFR and blood sodium in patients with pre-existing, compensated chronic renal failure (stage III), who are monitored for these parameters by their treating physicians.

Any subsequent imaging during the study period will be uploaded to the core lab. Timing and frequency of subsequent CT- or MR examinations vary in clinical practice. In case the 36 ( $\pm 6$ ) months' time point is not sampled in a particular patient, the latest CTA/MRA prior to this date will be analysed. Patients with imaging using different imaging modalities (e.g. initial MRA vs. subsequent CTA) will be excluded from assessing the images for the primary endpoint and considered to be dropouts in the statistical analysis. However, for patients with several images of the same modality, an analysis for the time span between these two identical modalities may be permitted by the adjudication committee.

At each treatment visit, remaining trial medication will be collected, the number documented and the blisters will be sent back for disposal. New trial medication is provided for the next period.

End of treatment visit will be planned 36 months after inclusion of the last patient. The same procedures are performed as in treatment visits. Patients should be asked to continue study participation/ treatment until month 120 ( $\pm 30$  days) or end of study (whatever comes first).

In case of intolerable AEs/ SAEs, new visits will be planned by the investigator until the findings have been clarified or became stable.

All patients will have a CTA/MRA at least 36 ( $\pm 6$ ) months after randomization and preferably around the last follow-up visit as per standard of care. All images will be uploaded in a pseudonymised manner to a central server. Patients will be told to stop the IMP if there is no indication to continue (indications to continue are for example myocardial infarction, TIA, ischemic stroke), and be advised to visit a general practitioner for future blood pressure regulation. A letter will be sent to the general practitioner that the study has ended.

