- Existing or intended pregnancy, lactation in patients of the intervention group. If patients in the control group become subsequently pregnant and/or need to breastfeed after randomisation, they will not be excluded from the trial.

All patients who finish the study prematurely will be asked to attend a follow-up visit and to return unused trial medication. The patient must be asked to consent to this last examination. The withdrawal examination will be documented in the CRF.

If a patient does not come to a visit, the patient will be contacted and asked for information. If the patient wants to withdraw and agrees to give explaining reasons, the reason should be documented in the patients file and in the CRF.

In case of early withdrawal, the last aneurysm imaging will be used for the primary outcome analysis (*last observation carried forward*).

If a patient has severe side effects from one component of the intervention only, (e.g. severe orthostatic hypotension from intensive blood pressure control or major gastrointestinal bleeding from ASA), it can be decided to adjust or stop the component of the intervention causing the side effects, while continuing the other component of the intervention.

For documentation of AEs and SAEs see 8.1.6 and 8.2.

| Term                         | Definition   | Comment/ Sample  |
|------------------------------|--|--|
| Drop-out, study              | 
Participation terminated completely, including follow-up
 
Possible reasons:
 
 
• Patient withdraws consent: Withdrawal
 
• Patient moved/cannot be contacted
 
• Interventions cannot be performed due to medical reasons
 
• Non-compliance of patient
 
 
Drop-out after completion of study intervention:
Lost to follow-up
 
Final examination will be performed, if patient agrees. Study-Completion/ Withdrawal-form will be completed.
 | 
ITT-sample
 
ITT-sample (if study intervention completed)
  |
| Drop-out, study intervention | Termination of study intervention, follow-up once as per protocol.   | ITT  |
| Screening-failure            | 
Exclusion criteria given prior to screening / enrolment:
 
Patient will be recorded at screening list, but will not be provided with a patient number.
   | -  |

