#### Analysis Variables

##### Primary analysis variable:

- Aneurysm rupture (i.e. aneurysmal subarachnoid hemorrhage, SAH) or growth (increase in any aneurysm diameter by  $\geq 1$ mm) on serial imaging (either two MR or CT angiographies) within 36 +/- 6 months from randomization.

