### 9.2 Definition of Trial Population to be analysed

The primary analysis will be performed for the full analysis set which comprises all patients randomised into the trial. In this set, every patient is analysed according to the group randomised into. Exceptions to this rule can be made for patients for whom non-eligibility became apparent after randomisation, provided all three of the following conditions hold:

- The entry criterion was measured prior to randomisation;
- The detection of the relevant eligibility violations can be made completely objectively;
- All subjects receive equal scrutiny for eligibility violations; (This may be difficult to ensure in an open-label study, or even in a double-blind study if the data are unblinded prior to this scrutiny, emphasising the importance of the blind review.)

The safety set will comprise all patients who have received study medication at least once, and will allocate the patients to the treatment they actually received, regardless of randomisation.

For definition of “premature withdrawal”, “screening failure” and “drop-out” see 4.6.1.

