### 9.3 Statistical Methods

Baseline characteristics will be summarized as means with standard deviations or proportions, as appropriate. In the primary analysis we will quantify the treatment effect of a strategy aimed at risk factor modification by intensive blood pressure treatment, monitoring with a blood pressure measuring device, and acetylsalicylic acid (ASA) on the risk of aneurysm rupture or growth, which is an established surrogate for the risk of rupture, compared with standard blood pressure treatment and no ASA.

We will compare the occurrence of outcome events in the two groups in terms of the risk ratio (RR), which will be obtained by means of a Poisson model. The precision of the RR estimates will be described with 95% confidence intervals obtained from the Poisson model. Our primary analyses will be based on the intention-to-treat principle. Patients will be censored in case of death from causes other than aneurysm rupture. In addition to crude analyses, we will do an analysis adjusted for the main risk factors of the primary outcome: aneurysm size, shape, location, age and smoking status. For our secondary analyses in which the timing of the outcome event is not prespecified but all follow-up data are taken into account, we will calculate hazard ratios using Cox regression analyses. Final details will be specified in the Statistical Analysis Plan.

We plan the following subgroup analyses: age ( $\leq 55$  versus  $> 55$  years), sex, and type (with or without previous rupture of another aneurysm), size (1.0-4.0 mm versus  $\geq 4.1$  mm), aneurysm location (posterior communicating artery / anterior communicating artery / posterior circulation versus all other aneurysms) and morphology of aneurysm (regular versus irregular shape).

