#### *Budget Impact Analysis (BIA)*

The design of the budget impact analysis (BIA) will be a study of different scenarios of either or not introducing preventive medication for patients with an aneurysm. The BIA will be based on data collected alongside the clinical study. It will allow estimation of the financial consequences of introduction of both ASA treatment and intensive hypertension control from the perspective of different stakeholders involved. All cost items needed for the BIA will be derived directly from our economic data collection, the valuation of those items depends on the perspective taken for the budget impact analysis. The perspectives to be included in the BIA are (1) net-BKZ or government perspective and (2) the health insurance perspective. Substitution effects, i.e. reduced need for expensive health care after aneurysm rupture will be taken into account. Different scenarios with different levels of implementation of preventive treatments will be analysed and compared, ranging from all patients with a known aneurysm, to patients with larger aneurysms only. The time horizon for the BIA will be 3 years. BIA results will be reported separately for each year within the time horizon and indexation will be applied.

Biometric analysis will be defined in the statistical analysis plan, which has to be authorised before opening the database by the biometrician, the sponsor, and the LKP.

The adjudication committee (PIs and another experts) will review protocol deviations and reach consensus on whether these should be regarded as major or minor, using blinded data if possible.

In addition, this committee will review unclear endpoints, such as sudden deaths and subarachnoid haemorrhage of unknown origin.

Subjects to be included in the analyses are all subjects randomised and thus a full intention to treat analysis.

The additional data provided by patients of the intervention group using blood pressure devices may be displayed in tables for descriptive statistics. They may be examined for their relationship with blood pressure values obtained during trial visits, for description of device utilisation, and for their relationships with outcomes as described above.

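### Section 6.3 makes patients whose scan modality changes dropouts from the statistical analysis, which conflicts with the all-randomised primary analysis and has no exception for rupture

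*Protocol*

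**What the plan says.** Section 6.3 (Treatment Visits) states that patients whose images come from different modalities, for example MRA first and CTA later, "will be excluded from assessing the images for the primary endpoint and considered to be dropouts in the statistical analysis". One relief follows: where a patient has several images of one modality, "an analysis for the time span between these two identical modalities may be permitted by the adjudication committee".

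The analysis sections say something else. Section 9.2: "The primary analysis will be performed for the full analysis set which comprises all patients randomised into the trial". Its single exception reads "Exceptions to this rule can be made for patients for whom non-eligibility became apparent after randomisation", and it requires that the entry criterion was measured before randomisation. Section 9.3: "Our primary analyses will be based on the intention-to-treat principle". The closing text of 9.3, under the budget impact heading, repeats it: "Subjects to be included in the analyses are all subjects randomised and thus a full intention to treat analysis".

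Section 4.6.1 adds a third instruction: "In case of early withdrawal, the last aneurysm imaging will be used for the primary outcome analysis". Its table of terms assigns drop-outs to the ITT sample. Section 9.1 uses the word differently again: 776 are assigned, with 10% dropout, so that 706 can be analysed.

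The primary analysis variable in 9.1 is rupture, or growth of at least 1 mm, "on serial imaging (either two MR or CT angiographies) within 36 +/- 6 months from randomization".

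**The concern.** Whether a patient is in the primary analysis should not depend on something that happens after randomisation. Here it may depend on the modality of a later scan. The trial schedule leaves that choice to standard of care, section 5.6 says that patients and investigators are unblinded, and nothing asks sites to keep the baseline modality.

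Two features make this more than untidy wording. First, the rule is attached to the primary endpoint as a whole, although only the growth component needs two comparable scans. Section 2.1 refers to CT imaging for suspected SAH. If a CTA is done at that moment (an assumption), a patient with a baseline MRA who ruptures falls within the words of the rule. Second, the way back into the analysis is case by case. Section 9.3 describes the adjudication committee as the PIs and other experts and promises blinded data for its review of protocol deviations only where possible. Section 6.3 sets no blinding condition for this permission.

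At stake are the denominator of the primary risk ratio, some of its events, and possibly its power.

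**Working it through.** **1. The conflicting instructions side by side**, for a patient with a baseline MRA and a later CTA:

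| Section | What happens to the patient |
|---|---|
| 6.3 | Images not assessed for the primary endpoint; a dropout in the statistical analysis |
| 9.1 | Dropouts are the difference between 776 assigned and 706 analysed, so not analysed |
| 4.6.1 | Drop-outs belong to the ITT sample; on early withdrawal the last imaging is used |
| 9.2, 9.3 | Analysed as randomised; a later modality change does not meet the only exception |

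A patient who withdraws early and whose last scan is of the other modality shows the clash most clearly: 4.6.1 uses that scan and 6.3 forbids it. If the patient is kept, no section says what primary outcome is assigned.

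**2. The plan's own sample size.** Inputs from 9.1: p1 = 0.15, p2 = 0.0825, alpha 0.05 (taken as two-sided), power 80%. The pooled-variance formula is

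n = [1.960·√(2·p̄·(1−p̄)) + 0.842·√(p1(1−p1) + p2(1−p2))]² / (p1−p2)², with p̄ = 0.11625.

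This is (0.888 + 0.379)² / 0.0675², which rounds up to 353 per group, as stated. Total: 706 × 1.1 = 776.6, matching 776.

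**3. Power if modality changes are additional to the 10% dropout.** The number per arm is 388 × 0.9 × (1−m), where m is the share lost through a modality change. The protocol gives no value, so m is an assumed range. Power = Φ{[0.0675·√n − 0.888] / 0.451}.

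| m (assumed) | n per arm | Power | Expected events lost, m × 349.2 × (0.15 + 0.0825) |
|---|---|---|---|
| 0% | 349 | 79.6% | 0 |
| 5% | 332 | 77.5% | about 4 |
| 10% | 314 | 75.3% | about 8 |
| 20% | 279 | 70.3% | about 16 |

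If these patients are already inside the 10%, the first row applies and nothing more is lost.

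**4. When the risk ratio would move.** Let e be the excluded share of patients with an event and q that of patients without one. The observed risk in an arm is p(1−e) / [p(1−e) + (1−p)(1−q)]. All values of e are illustrative, with q = 5% in both arms.

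- Exclusion unrelated to outcome: RR stays 0.0825/0.15 = 0.55.
- e = 20% in both arms: 0.0704/0.1294 = 0.54.
- e = 20% treated, 5% control: 0.0704/0.15 = 0.47.
- e = 5% treated, 20% control: 0.0825/0.1294 = 0.64.
- No true effect (15% in both arms), e = 20% treated, 5% control: 0.1294/0.15 = 0.86.

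Material bias needs exclusion that depends on both outcome and arm.

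**The case against.** Several points on the other side have force.

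*The same-modality requirement is part of the endpoint.* With a 1 mm threshold, refusing to compare an MRA with a CTA is a sensible measurement safeguard. This stands, and the fix keeps it. What it does not justify is turning an unmeasurable growth status into possible removal of the patient.

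*Removal is only one reading.* A reader might infer from 6.3 that these patients are definitely deleted. Section 4.6.1 can be read as keeping them, and 9.1 points the other way. The documents support a conflict, not a settled exclusion.

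*Ruptures are not shown to be discarded.* The sentence in 6.3 speaks of assessing images, and 2.1 gives rupture its own routes: central blinded assessment, committee review of suspected SAH with negative CT, and review of sudden deaths. Nowhere is an adjudicated SAH said to be dropped. What remains is that 6.3 contains no clause protecting it. The possible share is also limited. Section 3.1 puts the 5-year rupture risk at usually below 3%; at a constant rate that is at most about 3% × 3/5 = 1.8% in three years, or 1.8/15 = 12% of control-arm events. That is a ceiling on all ruptures, not an estimate of those affected.

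*The power loss may be counted twice.* Section 6.3 calls these patients dropouts and 9.1 already budgets for dropouts. Section 7.2.1 also expects imaging every one or two years in many centres, so some patients will have a same-modality pair. The power figures are therefore conditional.

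*Arm-related exclusion is conjecture.* One might infer that acute kidney injury under intensive blood pressure lowering, reported in section 1.3 from another trial population, would shift one arm away from contrast CTA. Section 1.3 gives no rate for it, and nothing links it to the modality of later routine scans.

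*Details may go to the SAP.* That is right for the imputation model. It does not cover a rule that the protocol states and contradicts.

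**Conclusion.** The point holds as a contradiction that governs who enters the primary analysis. Section 6.3 cannot be applied together with 9.2 and 9.3. Section 4.6.1 and section 9.1 pull the term dropout in opposite directions. The trigger occurs after randomisation in an open trial, rupture is not exempted, and rescue is discretionary.

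Its size is not known, because the protocol gives no modality-change rate. Power ranges from no further loss (changes within the 10% allowance) to about 77.5%, 75.3% or 70.3% at assumed additional rates of 5%, 10% or 20%. The risk-ratio shifts in the working show what outcome- and arm-dependent exclusion could do; they do not predict that it will happen. The documents do not support saying that ruptures will be deleted, that the trial is underpowered, or that the result will be biased.

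The matter should still be settled in the protocol before outcome data are compared by arm, because it decides which patients and events are counted and the correction is cheap.

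**What to change.** Amend the paragraph in 6.3 and align it with 4.6.1, 9.1, 9.2 and 9.3:

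1. Limit the same-modality rule to the measurement of growth, and remove the statement that these patients are dropouts in the statistical analysis.
2. Count every adjudicated rupture as a primary event, whatever the imaging modality.
3. Keep all randomised patients in the primary analysis, subject only to the exception already in 9.2.
4. Replace committee permission with a fixed rule applied blind to allocation: compare the baseline scan with the last scan of the same modality up to the end of the 36 ± 6 month window. Use a same-modality pair that starts after baseline only in a sensitivity analysis. With a baseline MRA and CTAs at months 12 and 36, for example, the CTA pair misses growth in the first 12 months.
5. Where no valid pair exists, treat growth status as missing and handle it by a prespecified method such as multiple imputation, with a sensitivity analysis. The model can sit in the SAP.
6. State in 4.6.1 and 9.1 whether dropouts are analysed, and whether the 10% allowance includes patients without a valid scan pair.

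The cost is a short amendment, some imputation work, and a few patients whose growth status is imputed rather than observed. No extra scans are needed.

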|                       | 
Exclusion Criteria
 
 
All non-saccular UIAs or aneurysms related to arteriovenous malformations
 
Daily ASA already prescribed for another indication
 
Use of a vitamin K antagonist or direct oral anticoagulant (DOAC) at baseline
 
History of hypersensitivity/allergy to ASA or to any other drug with similar chemical structure or to any excipient present in the pharmaceutical form of ASA
 
History of asthma induced by ASA or other anti-inflammatory drugs
 
Other contra-indications for low-dose ASA (81 mg - 100 mg per day) not yet mentioned, (e.g. bleeding disorders, , gastric ulcers and/or intestinal ulcers, acute liver failure of kidney failure, severe heart failure, treatment with methotrexate in a dosage 15 mg/week or above)
 
Use of another platelet aggregation inhibitor, which in combination with ASA would give an unacceptable risk of side effects/complications
 
Chronic kidney disease stage IV and V (GFR < 30 mL/min/1.73 m^2)
 
Pregnancy and lactation
 
Participation in any other interventional clinical trial
 
Life-expectancy <3 years
 
 |
| SAMPLE SIZE    | 
To be assessed for eligibility: (n = 2500)
 
To undergo screening examination: (n=970)
 
To be assigned to the trial: (n = 776)
 
To be analysed: (n = 705)
 
Assuming a risk reduction of 45% for the primary outcome measure and the risk to have a primary outcome event at three years of 15% in the standard treatment group and 8.25% in the intensive treatment + ASA group, <math>\alpha=0.05</math> and <math>\beta=0.20</math>, 353 patients are needed in each group. Assuming a dropout rate of 10%, we will need to assign 776 patients to the trial so that 705 patients can be analysed.
  |
| TRIAL DURATION | 
Total trial duration: [162 months]
 
Duration of clinical phase: [144 months]
 
Beginning of the preparation phase: [Q2 2017]
 
FSI (first subject in): [Q3 2017]
 
LSI (last subject in): [Q2 2026]
   |

|                             |  |
|-----------------------------|--|
|                             | LSO (last subject out): [Q2 2029]
DBL (database lock): [Q3 2029]
Statistical analyses completed: [Q4 2029]
Trial report completed: [Q2 2030]  |

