## CLINICAL TRIAL SCHEDULE

| Visit No.                                    | Visit 0                      | Visit 1        | Visit 2              | Visit 3 - 20               | Visit 21                                      | Visit 22  |
|--|------------------------------|----------------|----------------------|----------------------------|---|---|
|  | Screening*                   | Baseline       | Treatment phase      |                            | End of treatment/
study                    | Follow-up   |
| Day  | 0 – 30 days prior to visit 1 | Day 0          | 6 months +/- 30 days | every 6 months +/- 30 days | Month 36 +/- 30 days or month 120 +/- 30 days | 30 +/- 10 days after end of treatment visit (or after withdrawal) |
| Procedure                                    |                              |                |                      |                            |   |   |
| Written informed consent                     | ● (S)**                      |                |                      |                            |   |   |
| Inclusion/ exclusion criteria                | ● (S)                        | ●              |                      |                            |   |   |
| Demographic data, vital signs                | ●                            |                |                      |                            |   |   |
| Medical history                              | ● (R)**                      |                |                      |                            |   |   |
| Smoking status and alcohol consumption       | ●                            | ●              | ●                    | ●                          | ●   | ●   |
| Randomization                                |                              | ●              |                      |                            |   |   |
| Pregnancy test                               | ●  (S)           | ●  |                      |                            |   |   |
| Concomitant medication                       | ● (R)                        | ●              | ●                    | ●                          | ●   | ●   |
| AE   |                              | ●              | ●                    | ●                          | ●   | ●   |
| Aneurysm/ baseline characteristics           |                              | ●              |                      |                            |   |   |

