## **3.2 Trial Duration and Schedule**

The duration of the trial for each subject is expected to be at least 36 months intervention and one-month follow-up. For those subjects enrolled early in the trial, the intervention will be continued until the last subject enrolled completed the 36 months of intervention (maximum duration of treatment 120 months ± 30 days).

The overall duration of the trial is expected to be approximately 162 months. Recruitment of subjects has been started in in Q3 2017 in Germany. The actual overall or recruitment duration may vary. Based on a planned interim analysis, the DSMB can recommend modifying the duration of the trial. The study end is defined as "last patient out" (LPO), this may apply as well to a follow-up visit, if appropriate.

|  |                    |
|--|--------------------|
| Duration of the clinical phase for each patient: | [up to 120 months] |
| Total trial duration:                            | [162 months]       |
| Duration of clinical phase:                      | [144 months]       |
| Beginning of the preparation phase:              | [Q2 2017]          |
| FSI (first subject in):                          | [Q3 2017]          |
| LSI (last subject in):                           | [Q2 2026]          |
| LSO (last subject out):                          | [Q2 2029]          |
| DBL (database lock):                             | [Q3 2029]          |
| Statistical analyses completed:                  | [Q4 2029]          |
| Trial report completed:                          | [Q2 2030]          |

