## 7.2 Efficacy Parameters

### Primary efficacy endpoint:

- Aneurysm rupture (i.e. aneurysmal subarachnoid hemorrhage, SAH) or growth (increase in any aneurysm diameter by  $\geq 1\text{mm}$ ) on serial imaging (either two MR or CT angiographies) within 36 +/- 6 months from randomization.

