#### 7.2.1 Progression-free Survival

Progression-free survival, defined as the time from randomization to the first observation of aneurysm growth or rupture, will be assessed every 12 months, based on available data such as subsequent imaging, until study end. During the course of the study, timing of subsequent imaging of the intracranial aneurysm will be at the discretion of the treating physician, since there are currently no guidelines in this respect. However, we anticipate that many centers will perform imaging every one or two years. If a patient is lost to follow up, progression-free survival is censored at the time of last imaging. No x-ray or other radiation is used for trial purposes only. However, if the patient undergoes examinations for medical reasons (such as routine control of aneurysm) such examinations may be used for a second assessment for trial purposes.

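### Section 6.3 asks every patient for a scan without an upper time limit and prefers it near the last visit, so a compliant site can leave the 30 to 42 month primary window unsampled

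*Protocol*

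**What the plan says.** - **Endpoint.** Section 7.2 defines growth or rupture "on serial imaging (either two MR or CT angiographies) within 36 +/- 6 months from randomization". Section 2.1, the synopsis and the analysis variables under section 9.1 use the same window.
- **Scan instruction.** Section 6.3 requires a CTA or MRA of all patients, no earlier than 36 (±6) months, and continues: "months after randomization and preferably around the last follow-up visit as per standard of care".
- **When the last visit is.** Section 6.3: "End of treatment visit will be planned 36 months after inclusion of the last patient". Section 3.2 adds a cap: "maximum duration of treatment 120 months ± 30 days". The Clinical Trial Schedule gives the end-of-treatment visit as "Month 36 +/- 30 days or month 120 +/- 30 days".
- **Routine imaging.** Section 7.2.1 leaves timing to the treating physician and says: "we anticipate that many centers will perform imaging every one or two years". The schedule has an at-least-yearly check for new imaging in the Visit 3 to 20 column. That row collects scans already made as standard of care; it does not order one.
- **Fallback.** Section 6.3 provides that if the 36 (±6) month "time point is not sampled in a particular patient, the latest CTA/MRA prior to this date will be analysed".
- **Sample size.** Section 9.1 assumes three-year risks of 15% and 8.25%, giving 353 per group.
- **Calendar.** Last subject in Q2 2026, last subject out Q2 2029, then "DBL (database lock): [Q3 2029" in the synopsis.

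**The concern.** A scan after month 42 cannot inform the primary endpoint, yet the wording of section 6.3 accepts one and, for most patients, prefers one. No other provision brings a scan into the window. The schedule has no primary-scan entry at month 36 for patients who continue, and the yearly check only uploads what exists.

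At stake is how many patients have an outcome that reflects three years of exposure. The three-year risk drives the sample size, and the interim analyses in section 9.4 are triggered by counts of patients with a three-year outcome assessment. An in-window scan that was not made cannot be recovered later.

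**Working it through.** **1. The plan's own figure.** Inputs from section 9.1: p1 = 0.15, p2 = 0.0825, alpha 0.05 (taken as two-sided), power 80%. Pooled-variance formula, no continuity correction:

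n = [1.960·√(2·p̄·(1−p̄)) + 0.842·√(p1(1−p1) + p2(1−p2))]² / (p1−p2)², with p̄ = 0.11625

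n = (0.888 + 0.379)² / 0.0675² = 352.8, so 353 per group. The stated size reproduces and is not in question.

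**2. Where the preferred time falls.** The end-of-treatment visit is a common calendar date, the last inclusion plus 36 months, capped at month 120. A patient enrolled t months before the last inclusion has that visit at month 36 + t, which lies after month 42 when t > 6. Q3 2017 to Q2 2026 is about 105 months, quarter midpoint to midpoint (102 to 108 at the extremes). With uniform recruitment (assumed):

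- last visit inside the window: 6/105 = 5.7%, about 44 of 776
- last visit after month 42: 94.3%, about 732 of 776 (94.1% to 94.4% across the extremes)
- median last visit: about month 87 to 90

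If the sentence means the 30-day follow-up visit instead, the second share is about 95%.

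**3. What routine imaging delivers.** Section 4.4 requires a scan within 3 months before randomisation. Counting intervals from that scan:

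| Routine interval | Months after randomisation | Inside 30–42? |
|---|---|---|
| Yearly, third scan | 33 to 36 | Yes |
| Two-yearly, first scan | 21 to 24 | No |
| Two-yearly, second scan | 45 to 48 | No |

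The two-yearly patient meets the minimum in section 6.3 through the second scan and is judged on the first.

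**4. Effect on power.** Let x be the share judged at month 24. Assume linear accrual (control risk 15% × 24/36 = 10% at month 24) and a constant 45% reduction. Then p1 = 0.15(1−x) + 0.10x and p2 = 0.55·p1, with 353 per arm:

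| x | p1 | p2 | Power |
|---|---|---|---|
| 0 | 15.0% | 8.25% | 80.0% |
| 10% | 14.5% | 7.98% | 78.5% |
| 25% | 13.75% | 7.56% | 76.0% |
| 50% | 12.5% | 6.88% | 71.5% |
| 100% | 10.0% | 5.5% | 60.9% |

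Linear accrual may be pessimistic. Section 3.1 gives growth of about 15% at 3 years and 18% at 5 years, so later accrual is slower: (18−15)/2 = 1.5 points per year. If that slower rate already applied in year three, the month-24 risk would be 15 − 1.5 = 13.5%, and power at x = 10%, 25% and 50% would be 79.6%, 78.9% and 77.7%. Clinically detected ruptures after month 24 need no routine scan, which also softens the loss slightly. Section 3.1 puts the five-year rupture risk usually below 3%, so that effect is small.

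**5. The last recruits.** Q2 2026 + 30 months = Q4 2028; + 36 = Q2 2029, the same quarter as last subject out; + 42 = Q4 2029, one quarter after the planned lock. This touches about 3/105 = 2.9% of patients (about 22) if lock comes at the same point of its quarter as last entry, and up to 6/108 = 5.6% (about 43) if lock is at the start of Q3. Their months 30 to 36 still precede lock.

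**The case against.** Five fair points can be made in favour of the plan.

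- **The month-36 anchor is there.** A reader might infer that the scan is tied to the end of the study and not to month 36. The text does not support that: the requirement itself refers to 36 (±6) months and the last-visit timing is only a preference. Section 9.4 also treats the 36-month visit as an outcome time. What stands is the absence of an upper limit and a preference that pulls the other way.
- **94% is not the share without an in-window scan.** A reader might take it so. It is only the share whose preferred scan time lies after month 42. Patients imaged yearly are sampled inside the window, and all routine scans are uploaded.
- **No outcome goes missing for this reason.** The fallback supplies an earlier scan, and a late scan still serves secondary endpoint 1. The harm is shorter exposure and fewer counted events.
- **The lock date does not shut out the last recruits.** They lose only the late part of a tolerance window, and section 3.2 says durations may vary. Waiving the follow-up visit in section 6.4 does not lose their images either, because the end-of-treatment column has its own imaging check.
- **Standard-of-care timing is deliberate.** Section 7.2.1 rules out radiation for trial purposes only. Any remedy must work within that, and re-timing a routine scan where local practice allows does so.

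These points narrow the concern. They do not remove the mismatch between the scan instruction and the endpoint window.

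**Conclusion.** The point holds in a limited form. Section 6.3 lets a site comply while leaving months 30 to 42 unsampled, and the fallback then replaces a three-year outcome with one at about two years.

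The size depends on the share of patients imaged every two years, which the protocol does not give. At 10% to 50% judged at month 24, power is 78.5% to 71.5% under linear accrual, or 79.6% to 77.7% if accrual in year three is already at the slower later rate. Both ranges assume 353 analysed per arm and a constant 45% reduction. If nearly all centres image yearly, the loss is negligible.

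The preference for the last visit conflicts with the window for about 94% of patients under uniform recruitment. That measures how widely the wording misdirects, not how many outcomes are affected. The lock date is a minor planning detail. The change is worth making because it is cheap.

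**What to change.** 1. Reword the sentence in section 6.3: each patient's routine CTA or MRA is timed between months 30 and 42 after randomisation where standard of care allows. Name a scan near the last follow-up visit separately, as preferred for secondary endpoint 1.
2. In the Clinical Trial Schedule, mark the month-36 visit as the check that the primary-window scan has been obtained and uploaded.
3. For patients recruited in about the last 6 months, time the scan between month 30 and the end-of-treatment visit. The database lock need not move.

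Cost: a wording and schedule amendment. Some two-yearly centres would shift a routine scan by up to about 6 months (for example from month 24 to 30, or from 48 to 42). The primary endpoint needs no extra scan, because section 6.3 already foresees one for every patient.
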